6.6.1. Unsolicited Treatment-emergent Adverse Events

A treatment-emergent AE (TEAE) is defined as any event occurring during the study not present before exposure to the IP or any event already present that worsens after exposure to study vaccine. Worsening of a pre-existing condition after vaccination will be reported as a new AE.

Adverse events will also be evaluated by the investigator for the coexistence of MAAE which is defined as an AE that leads to an unscheduled visit to a healthcare practitioner.

Unsolicited AEs will be coded by PT and SOC using MedDRA and summarized by vaccination group.

Unsolicited AEs will be collected for up to 28 days after each IP dose; SAEs, MAAEs, AEs leading to withdrawal will be collected throughout the study. Analyses of unsolicited AE will be provided for up to 28 days after any vaccination unless otherwise specified; and select analyses of unsolicited AE will be provided for Surveillance stage, and overall stage ([Section 6.1](#)).

All summary tables (except for the overall summary of AEs) for unsolicited AEs will be presented by SOC and PT or by PT only for TEAEs with counts of subjects included. SOC will be displayed in internationally agreed order. PT will be displayed in descending order of frequency of mRNA-1273 and then alphabetically within SOC. When summarizing the number and percentage of subjects with an event, subjects with multiple occurrences of the same AE or a continuing AE will be counted once. Only the maximum severity level will be presented in the severity summaries, and the strongest relationship level will be presented in the relationship summaries.

Unsolicited TEAE will be summarized up to 28 days after any injection. Unsolicited TEAEs may be summarized throughout the study and will be referred to as Overall stage (Part A), defined as from the first dose of study IP to the earlier date of (study discontinuation, study completion, death, data cutoff for safety, PDV/unblinding) for those who did not receive study IP in Part B; or from the first dose of study IP to the earlier date of (study discontinuation, study completion, death, data cutoff for safety, or 1st dose of study IP in Part B) for those who received study IP in Part B.

For AE events (Preferred Terms) with at least 7 participants in any treatment group who report the event, rate ratio and its 95% CI will be provided as a helpful descriptive measure to be used in review, not a formal method for assessing the statistical significance of the between-group differences in adverse experiences. The rate ratio is calculated as the ratio of percentage of participants reporting the event in mRNA-1273 divided by that in Placebo. The 95% CI for rate ratio will be provided using the Miettinen and Nurminen

method (1985). The threshold of at least 7 participants was chosen because the 95% CI for rate ratio will always include one when groups of equal size each have <7 participants reporting the event, and thus would add little for review purpose.

Percentages will be based upon the number of subjects in the Safety Set within each treatment group.

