4.4. Randomization

Approximately 30,000 participants will be randomly assigned in 1:1 ratio to receive either mRNA-1273 100 µg or placebo. The randomization will be in a blinded manner using a centralized Interactive Response Technology (IRT) at the Day 1 visit, in accordance with pre-generated randomization schedules. Participants will be stratified by age (≥ 18 and < 65 , or ≥ 65 years) and, if they are < 65 years of age, based on the presence or absence of risk factors for severe illness from COVID-19 based on recommendation by the US Centers for Disease Control and Prevention (CDC) as of March 2020. There will be 3 strata for randomization:

- ≥ 18 and < 65 years and not at risk
- ≥ 18 and < 65 years and at risk
- ≥ 65 years

At least 25% of enrolled participants, but not to exceed 50%, will be from the ≥ 65 years age group and < 65 years at risk group.

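### The 7-participant cut-off for AE rate ratios rests on a false statement: the planned Miettinen-Nurminen 95% CI excludes 1 at 4-0, 5-0 and 6-0

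*SAP*

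**What the plan says.** The rule is in the Part A SAP, Section 6.6.1. It applies to preferred terms "with at least 7 participants in any treatment group who report the event, rate ratio and its 95% CI will be provided". The measure is a simple ratio of percentages: "The rate ratio is calculated as the ratio of percentage of participants reporting the event in mRNA-1273 divided by that in Placebo". The denominator is the Safety Set of each group. The interval method is named: "The 95% CI for rate ratio will be provided using the Miettinen and Nurminen" method. The only reason given for the threshold is that "the 95% CI for rate ratio will always include one when groups of equal size each have <7 participants" reporting the event, so that showing the ratio below 7 would be of little use to a reviewer.

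The same paragraph calls the ratio "rate ratio and its 95% CI will be provided as a helpful descriptive measure to be used in review" and says it is not a formal test of the difference between groups. On group size, Section 4.4 states: "Approximately 30,000 participants will be randomly assigned in 1:1 ratio to receive either" mRNA-1273 or placebo, which is about 15,000 per arm.

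**The concern.** The justification is a mathematical claim about a named interval at a named level, so it can be checked. It looks wrong on sight. With equal arms and rare events, the score chi-square for a k-0 split is about k, and the 95% critical value is 3.84, so the interval should begin to exclude 1 at k = 4, not k = 7.

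The splits affected are those where every report falls in one arm. In a vaccine trial of about 30,000 people, rare one-sided events are where a comparative measure helps a safety reader most. A reader who trusts the SAP will also take a missing CI to mean that it would have covered 1. For these splits that inference is wrong.

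**Working it through.** **Inputs.**
- Threshold of 7, 95% level and Miettinen-Nurminen ratio interval: Part A SAP 6.6.1.
- Arm size n = 15,000 each: from 1:1 allocation of about 30,000, SAP 4.4. The Safety Set size per arm is assumed to be close to this.
- Two-sided critical value: chi-square on 1 df, 3.8415.

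**The plan's figure.** The SAP implies that 7 is the smallest count at which the 95% CI can exclude 1. This could not be reproduced, as steps 1 to 4 show.

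**Step 1: the statistic.** For a hypothesised ratio R,

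T(R) = (p1 − R·p2)² / V, with V = [q1(1 − q1)/n1 + R²·q2(1 − q2)/n2] · N/(N − 1),

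where q1 = R·q2 are the restricted maximum likelihood estimates and N = n1 + n2. The CI is the set of R with T(R) ≤ 3.8415.

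**Step 2: hand approximation for a k-0 split.** With equal arms and rare events, q2 ≈ k/[n(1 + R)] and q1 ≈ Rk/[n(1 + R)]. Then V ≈ kR/n² and T(R) ≈ k/R. Setting this equal to 3.8415 gives

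lower limit ≈ k/3.8415.

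The arm size cancels. For example, 4/3.8415 = 1.041. For the mirror split 0-k, the upper limit is about 3.8415/k.

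**Step 3: full calculation at n = 15,000 per arm**, using the N/(N − 1) factor:

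| Split | T at R = 1 | Score p | 95% CI | Mirror split, 95% CI |
|---|---|---|---|---|
| 3-0 | 3.00 | 0.083 | 0.781 to ∞ | 0 to 1.280 |
| 4-0 | 4.00 | 0.046 | 1.041 to ∞ | 0 to 0.960 |
| 5-0 | 5.00 | 0.025 | 1.302 to ∞ | 0 to 0.768 |
| 6-0 | 6.00 | 0.014 | 1.562 to ∞ | 0 to 0.640 |

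**Step 4: all other splits with both counts below 7.** At R = 1, T ≈ (a − b)²/(a + b). With at least one event in each arm the largest value is for 6-1: 25/7 = 3.57, below 3.84, with CI 0.949 to 37.9. So the statement fails for exactly 4-0, 5-0, 6-0 and their mirrors. The same set results without the N/(N − 1) factor and at the equal arm sizes tried from 50 to 15,200.

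**Step 5: could another method have produced 7?**
- Exact conditional test, two-sided p = 2 × 0.5^k: 0.125 (4-0), 0.0625 (5-0), 0.031 (6-0). It first excludes 1 at 6-0, with lower limit 1.177.
- Continuity-corrected chi-square, (k − 1)²/k: 3.20 at 5-0 and 4.17 at 6-0. First exclusion at 6-0.
- Log-Wald with 0.5 added: first exclusion at 9-0. The SAP sentence would be true under this method, but it is not the one specified.
- Miettinen-Nurminen at 99%: lower limit 0.905 at 6-0 and 1.055 at 7-0, so 7 is the first excluding count. The documents do not say that this is where the number came from.

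None of the 95% methods tried has 7 as its first excluding count.

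**The case against.** The case for leaving it alone is that little is lost. SAP 6.6.1.2 tabulates counts and percentages by system organ class and preferred term with no minimum count, so a 6-0 imbalance is visible, and an independent DSMB reviewed unblinded safety data. The ratio is descriptive only. In every vaccine-excess split where the statement fails, placebo has no events, so the point estimate is unbounded and only the lower limit carries information. The 4-0 result is marginal: it reverses once the arm with events is more than about 4% larger (4/3.8415 = 1.041). By the exact test only 6-0 falls below 0.05. A lower cut-off will display more chance findings, with no multiplicity adjustment for safety endpoints. Finally, the Part B and Part C SAP describes the Part A analyses as completed, and its own safety sections contain no such rule.

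Most of this stands as a limit on the impact, and none of it makes the sentence true. The unbounded estimate is no reason to stop at 7, because a 7-0 term has the same problem and is already admitted. The exact test does not support 4-0 or 5-0, but it is not the planned method, and even it contradicts the SAP at 6-0. A cut-off of 4 is what the SAP's own criterion yields once the arithmetic is corrected.

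**Conclusion.** The concern holds. The stated basis for the threshold is false for the method and confidence level that the SAP names: the correct bound is fewer than 4, not fewer than 7. The error is confined to six splits: 4-0, 5-0, 6-0 and their mirrors. The 5-0 and 6-0 results tolerate small differences in arm size; 4-0 needs nearly equal arms. Arm size itself is not a sensitive assumption, since it cancels.

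The consequence is that the ratio and CI are not shown for those terms. The counts themselves are not hidden. How many preferred terms are affected cannot be told from the documents. This is a definite but narrow error in a safety display rule, and worth correcting.

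**What to change.** Lower the cut-off to at least 4 participants in either group and restate the reason: with equal arms, the Miettinen-Nurminen 95% CI includes 1 whenever both counts are below 4. Keep the statement that the ratios are descriptive. Say how a term with a zero count in one arm is displayed (for example, the finite limit only), which Section 6.6.1 does not cover and which 7-0 terms already need. Since Part A has been reported, the practical form is a correction note plus a supplementary table, from existing data, of terms whose larger group count is 4 to 6. If the sponsor prefers to keep 7, it should be called a display convention and the mathematical claim removed.

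The cost is one sentence and extra rows in a descriptive table. More chance imbalances will appear. With equal risk in equal arms, a term with four reports in total splits 4-0 or 0-4 with probability 2 × 0.5⁴ = 12.5%, one with five splits wholly one way with probability 6.25%, and one with six with probability 3.1%. A footnote to that effect would guard against over-reading.

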6.6.1.1. Overview of Unsolicited TEAEs

An overall summary of unsolicited TEAEs including the number and percentage of subjects by treatment group who experience the following will be presented:

- Any unsolicited TEAEs
- Any serious AEs
- Any unsolicited AEs that are medically-attended
- Any unsolicited TEAEs leading to discontinuation from participation in the study
- Any unsolicited severe TEAEs (severity of AEs is assessed as mild, moderate and severe)
- Any unsolicited TEAEs that are fatal

The table will also include number and percentage of subjects with unsolicited TEAEs that are treatment-related in each of the above categories.

The overall summary will be provided for unsolicited TEAE up to 28 days after any injection, and for the Overall Stage throughout Part A respectively.

In addition, separate listings containing individual subject adverse event data for unsolicited TEAEs leading to discontinuation from study vaccine, unsolicited TEAEs leading to discontinuation from participation in the study, serious AEs, serious treatment-related AEs, and unsolicited treatment-related medically-attended AEs may be provided. Listing of deaths including cause of death, and listing of TEAEs in subjects who died will be provided.

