As noted above, this is a case-driven study: if the prespecified criteria for early efficacy are met at the time of either IA or overall efficacy at the primary analysis, a final study report describing the efficacy and safety of mRNA-1273 will be prepared based on the data available at that time. In the event that success criteria are met either at the time of the IA or when the total number of cases toward the primary endpoint have accrued, participants will continue to be followed in a blinded fashion until Month 25 to enable assessment of long-term safety and durability of VE.

If the study concludes early, all participants will be requested to provide a final blood sample at the time of study conclusion.

Each participant will receive 2 doses of IP by 0.5 mL intramuscular (IM) injection, the first on Day 1 and the second on Day 29. An NP swab sample will be collected prior to the first and second dose of IP, for evaluation by RT-PCR. Participants will be given an electronic diary (eDiary) to report solicited adverse reactions (ARs) for 7 days after each dose of IP and to prompt an unscheduled clinic visit for clinical evaluation and NP swab sample if a participant experiences any symptoms of COVID-19 (throughout study). All participants will receive safety calls on Day 8, Day 15, Day 22, Day 36, and Day 43

that will serve both to monitor for unsolicited adverse events (AEs) and to monitor for symptoms of COVID-19.

Surveillance for COVID-19 will be performed through weekly contacts with the participant via a combination of telephone calls and completion of an eDiary starting at Day 1 through the end of the study.

Participants with symptoms of COVID-19 lasting at least 48 hours (except for fever and/or respiratory symptoms) will return to the clinic or will be visited at home by medically qualified site staff within 72 hours (an “Illness Visit”) to collect an NP swab sample for RT-PCR testing for SARS-CoV-2 and other respiratory pathogens, or alternatively, if a clinic or home visit is not possible, will submit a saliva sample for SARS-CoV-2 RT-PCR testing. Any confirmed COVID-19 occurring in a participant will be captured as a medically attended AE (MAAE) along with relevant concomitant medications and details about severity, seriousness, and outcome. All confirmed serious COVID-19 cases will be reported to the Sponsor or designee within 24 hours.

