If scheduled, a study site Illness Visit includes assessments such as medical history, physical examination, blood sampling for clinical laboratory testing, and 2 NP swabs, 1 for viral polymerase chain reaction (PCR) SARS-CoV-2 testing and 1 for multiplex PCR testing for respiratory viruses, to evaluate the severity of the clinical case. Radiologic imaging studies may be conducted. Blood samples will be collected for potential future immunologic assessment of SARS-CoV-2 infection. Every effort to complete an Illness Visit that includes both the NP swabs and blood draw should be made by the site, even in the presence of a local positive or negative Clinical Laboratory Improvement Amendments (CLIA) certified or CLIA-certified waiver laboratory result for the participant.

Cases are defined as participants meeting clinical criteria based both on symptoms for COVID-19 and on RT-PCR detection of SARS-CoV-2 from samples collected within 72 hours of the study participant reporting symptoms meeting the definition of COVID-19. Participants who are hospitalized for COVID-19 without the opportunity for a clinic or home visit will also be considered cases, assuming that the symptomatology criteria for COVID-19 are met and a respiratory sample is positive for SARS-CoV-2 by PCR at a CLIA-certified or CLIA-certified waiver laboratory. Investigators are encouraged to try to obtain a respiratory sample during the course of hospitalization for submission to the study central laboratory, if feasible. The investigator should determine if the criteria for severe COVID-19 has been met.

Evidence of severe COVID-19 is defined as in [Section 8.1.1](#).

All clinical findings will be recorded in the eCRF. All confirmed cases of COVID-19 will be captured as MAAEs, along with relevant concomitant medications and details about severity, seriousness, and outcome.

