11.5. APPENDIX 5: Adverse Events of Special Interest Terms

The **Investigator’s medical judgement must be applied** to assess an event as an AESI, as most AESIs are based on medical concepts. Table 27 below does not provide a comprehensive list of terms.

Table 27 describes events/medical concepts that are of interest in COVID-19 vaccine safety surveillance. Some are specific to vaccines; however, some are of interest due to their occurrence in the context of concurrent or recent COVID-19. Events that occur in Part C (after participants receive a booster dose) and fall into the descriptions below should be reported as AESIs, per the reporting processes specified in [Section 8.3.3](#), even when they occur during/following COVID-19 infection.

Please note: COVID-19 itself is not an AESI.

Table 27: Adverse Events of Special Interest

Medical Concept	Medical Concept Descriptions/Guidance
Anosmia, Ageusia	
 • New onset of anosmia or ageusia associated with COVID-19 or idiopathic etiology • DOES NOT INCLUDE anosmia or ageusia associated with sinus/nasal congestion, congenital, or traumatic etiologies
Subacute thyroiditis	
 • Acute inflammatory disease of the thyroid (immune-mediated or idiopathic) • DOES NOT INCLUDE new onset of chronic thyroiditis
Acute pancreatitis	
 • New onset of pancreatitis in the absence of a clear, alternate etiology, such as alcohol, gallstones, trauma, recent invasive procedure, etc.
Appendicitis	
 • Any event of appendicitis
Rhabdomyolysis	
 • New onset of rhabdomyolysis in the absence of a clear, alternate etiology, such as drug/alcohol abuse, excessive exercise, trauma, etc.
Acute respiratory distress syndrome (ARDS)	
 • New onset of ARDS/respiratory failure due to acute inflammatory lung injury • DOES NOT INCLUDE non-specific symptoms of shortness of breath or dyspnea, nor events with underlying etiologies of heart failure or fluid overload
Coagulation disorders	
 • New onset of thrombosis, thromboembolic event, or non-traumatic hemorrhage/bleeding disorder (ex. stroke, DVT, pulmonary embolism, disseminated intravascular coagulation (DIC), etc.)

Medical Concept	Medical Concept Descriptions/Guidance

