If a subject received any dose of mRNA-1273 at any injection, regardless of the treatment group the subject was randomized to, the subject will be included to mRNA-1273 100 µg group as the actual treatment group received for safety analyses.

All analyses and data summaries/displays for disposition, baseline demographics and characteristics will be provided by Baseline SARS-CoV-2 Status (negative, positive, and overall) and treatment group unless otherwise specified. All analyses and data summaries/display for efficacy will be provided by treatment group using appropriate analysis population unless otherwise specified.

Analysis Periods

The following analysis periods and treatment groups will be used for efficacy analyses for the blinded phase (Part A):

Part A Group	Description	Blinded/Part A Analysis Period for Efficacy
mRNA-1273	Participants randomized to mRNA-1273 in the Blinded Phase	From randomization to earlier date of Participant Decision Visit (PDV)/unblinding, study discontinuation, study completion, death, or data cutoff date for efficacy)
Placebo	Participants randomized to Placebo in the Blinded Phase	

The analysis period and treatment groups of the blinded phase (Part A) for Safety analyses is summarized below:

Part A Group	Description	Blinded/Part A Analysis Period for Safety
--------------	-------------	---

mRNA-1273	Participants received at least one dose of mRNA-1273 in the Blinded Phase	From the first dose of study IP to the earlier date of (study discontinuation, study completion, death, data cutoff for safety, PDV/unblinding) for those who did not receive study IP in Part B. For participants received study IP in Part B, from the first dose of study IP in study to the earlier date of (data cutoff for safety, or 1st dose of study IP in Part B)
Placebo	Participants only received Placebo in the Blinded Phase	

The above analysis period for safety analysis in Part A is also referred to as Overall Period in Part A. For Part A, up to 28 days after any vaccination, starts at the day of each vaccination and continue through the earliest date of (the day of each vaccination and 27 subsequent days, next vaccination [if applicable]), will be used as the primary analysis period for safety analyses including unsolicited AE, except for solicited AR, unless specified otherwise.

Part B

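### The pooled Overall Stage AE rows count COVID-19 itself as an adverse event, mainly on placebo, and no version without it is planned

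*SAP*

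**What the plan says.** - **Recording.** Protocol 8.1.2: "All confirmed cases of COVID-19 will be captured as MAAEs". The synopsis repeats the rule, and Protocol 8.3.2 names COVID-19 among the visits that make an event an MAAE. Under Protocol 8.3.8 and 8.3.11, cases that meet the seriousness criteria are reported as SAEs are. Amendment 8 narrowed 24-hour reporting to serious cases; it did not stop COVID-19 being recorded as an MAAE.
- **Collection period.** SAP Part A 6.6.1: "SAEs, MAAEs, AEs leading to withdrawal will be collected throughout the study". SAP Part A 3.1.2 makes MAAEs and SAEs primary safety endpoints over the whole study.
- **Tables.** SAP Part A 6.6.1.1 gives, by arm, participants with any TEAE, any SAE, any severe TEAE, any fatal TEAE and "Any unsolicited AEs that are medically-attended". The table is produced for 28 days after any injection "and for the Overall Stage throughout Part A respectively". SAP Part A 6.6.1.2 adds SOC and preferred-term tables. SAP Part B/C 5.4.1.1 and 5.4.1.2 do much the same by cohort.
- **Primary safety period.** SAP Part A 6.1 says that the 28 days after any vaccination "will be used as the primary analysis period for safety analyses including unsolicited AE".
- **Between-arm measure.** SAP Part A 6.6.1 plans rate ratios with 95% CIs by preferred term only, and calls them descriptive.
- **Part C AESIs.** Protocol 11.5 states that COVID-19 is not itself an AESI, but that listed events are reported as AESIs "even when they occur during/following COVID-19 infection".

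Neither SAP excludes COVID-19 from a pooled row or plans a second version without it.

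**The concern.** A pooled row counts each participant with at least one qualifying event. If COVID-19 qualifies, an effective vaccine lowers the row for any MAAE and any TEAE simply by preventing the disease. Protocol 2.3.2 reports that the overwhelming majority of cases were on placebo, so the direction is known: the placebo percentage is raised and the contrast moves in the vaccine's favour. A real excess of other medically attended events on vaccine, if no larger than that shift, would show as no difference in the row. The SOC total that contains COVID-19 is affected in the same way.

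The COVID-19 preferred-term line does not let the reader undo this exactly. Some participants with COVID-19 also have another MAAE and are counted once, so the rate without COVID-19 cannot be found by subtraction.

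**Working it through.** **Inputs.** About 30,000 participants at 1:1, so about 15,000 per arm (Protocol 6.2.1). Planning rates of 0.75% (placebo) and 0.30% (vaccine) over 6 months (Protocol 9.3, Table 6). 196 adjudicated per-protocol cases from 14 days after dose 2, cut at 21 Nov 2020 (SAP Part A 6.4.2.2). VE 94.5% on 95 cases at the interim analysis (SAP Part B/C Introduction). The documents give neither the arm split of the 196 cases nor a background MAAE rate, so two assumptions are needed: the interim VE carries over, and the background rate b without COVID-19 lies between 5% and 30%.

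**Step 1: the plan's own figure.** With v(h) = (1+h)²/h, the fixed-design number of events is [1.960·√v(0.7) + 1.282·√v(0.4)]² / [ln(0.4/0.7)]² = 148.5. Multiplied by the O'Brien-Fleming-type spending inflation of 1.014, this is 150.6, which reproduces the stated 151. The vaccine rate 0.75% × (1 − 0.60) = 0.30% also reproduces. The planning rates can be used as they stand.

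**Step 2: gap in the case rates.**
- Planning, 6 months: 0.0075 × 15,000 = 112.5 v 0.0030 × 15,000 = 45. Gap 0.45 points.
- 196 cases: vaccine share = 0.055/1.055 = 0.052, so 10.2 on vaccine and 185.8 on placebo. Gap 175.6/15,000 = 1.17 points.

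These are upper limits for the shift in the any-MAAE row, because they suppose that no case had another MAAE.

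**Step 3: allowing for overlap.** Take COVID-19 as independent of other MAAEs, with case rates cP (placebo) and cV (vaccine). The placebo any-MAAE rate is 1 − (1−b)(1−cP). The true vaccine excess that would leave the two arms equal is (1−b)(cP−cV)/(1−cV).

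| Background b | Hidden excess, planning | Hidden excess, 196 cases | 95% CI half-width of difference |
|---|---|---|---|
| 5% | 0.43 | 1.11 | 0.49 |
| 10% | 0.41 | 1.05 | 0.68 |
| 20% | 0.36 | 0.94 | 0.91 |
| 30% | 0.32 | 0.82 | 1.04 |

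All entries except b are percentage points. The half-width is 1.96·√[2b(1−b)/15,000]. The 196-case shift exceeds sampling noise at 5% and 10%, about equals it at 20% and is below it at 30%. The planning-rate shift is below it throughout.

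**Step 4: what removing COVID-19 would gain.** With COVID-19 out of the row, the power (2-sided 5%) to see the 196-case excess is 99%, 85%, 52% and 34% at the four background rates. For the planning-rate excess it is 39%, 21%, 12% and 9%.

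**Step 5: the primary 28-day period.** Two windows are at most 56 days. At the planning rate, placebo incidence is 0.75% × 56/182.5 = 0.23%. The gap is 0.23% × 0.60 = 0.14 points at VE 60%, and 0.22 points at VE 94.5%.

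**Step 6: more serious rows.** The only related count is 11 adjudicated severe COVID-19 cases in both arms together at the interim analysis (SAP Part A 6.5). Even if all were on placebo, that is 11/15,000 = 0.07%. Severe COVID-19 is not the same as an SAE or a severe AE, and the count will have grown, so this indicates scale only.

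**The case against.** The strongest reply is that the shift sits where it does least harm. In the primary 28-day period it is 0.1 to 0.2 points. A vaccine-related excess would be sought first in the preferred-term rate ratios and the SOC and preferred-term tables. Rows for other terms are untouched, the treatment-related counts hardly move, and deaths are listed with cause. Safety is judged by clinical review and the rate ratios are descriptive, so no formal test is biased. The COVID-19 preferred-term line also caps the offset in each arm, which bounds the non-COVID rate even though it does not give it. All of this stands. It does not remove the point, because MAAEs and SAEs are primary safety endpoints over the whole study, which makes the Overall Stage their natural window.

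A reader might go further in three directions that the documents do not support.
- **That SAE, severe and fatal rows are shifted by a similar amount.** The direction is the same, but no figure in the documents supports that size, and Step 6 suggests that the effect is probably small.
- **That Part C has the same efficacy offset.** The Part C Safety Set contains booster recipients only, so there is no randomised contrast to shift. Pooled rates there may follow community incidence, which is a matter of description.
- **That COVID-19 itself inflates the AESI table.** Protocol 11.5 says that COVID-19 is not an AESI. It deliberately includes some concepts because they occur with COVID-19.

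Timing also counts. SAP Part B/C states that the Part A analyses are considered complete, with a CSR dated 03 August 2021.

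**Conclusion.** The concern holds for the Overall Stage rows for any MAAE and any TEAE and for the SOC total that contains COVID-19. As planned, those rows include the efficacy endpoint, mainly on placebo, and no companion row allows the reader to set it aside.

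The gap is up to 1.17 points for the 196 cases. After overlap, it could conceal a true vaccine excess of about 0.8 to 1.1 points, or about 0.3 to 0.4 points at planning rates. This rests on the interim VE applying to all 196 cases, on background MAAE rates of 5% to 30%, on independence of COVID-19 and other MAAEs, and on 15,000 per arm. The Safety Set tables run from the first dose to the end of blinded follow-up, whereas the 196 cases start 14 days after dose 2 and stop at an early cut. The final gap is therefore probably larger, but the documents do not allow it to be calculated.

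**What to change.** Keep the all-inclusive tables. Beside them, add pooled rows for any TEAE, MAAE, SAE, severe and fatal event that exclude a predefined list of COVID-19 and SARS-CoV-2 infection preferred terms:

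- in SAP Part A 6.6.1.1 and 6.6.1.2, for both periods, as a supplementary output labelled as added after Part A reporting;
- in SAP Part B/C 5.4.1.1 and 5.4.1.2, by cohort.

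Limit the exclusion to the listed terms. Removing events judged to be complications of COVID-19, or making the exclusion tables primary, would bring in judgement made after unblinding and is not needed here.

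In Part C, as a descriptive addition only, show AESIs by whether they began during or after a confirmed post-booster SARS-CoV-2 infection. The planned subgroup by pre-booster status does not capture this.

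The cost is one term list fixed in advance and one more run of existing tables. No new data are needed and no existing result changes.
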